The target population for the program consists of children referred to the Child development Unit at National University Hospital, a tertiary care hospital. Children in the target population meeting all the inclusion criteria will be eligible to enrol in the evaluation study. They will be excluded if they meet any of the exclusion criteria. We will not be advertising this study to the public.

Recruitment: Children found to be at risk for Autism Spectrum Disorders (ASD) on clinical evaluation by Developmental Paediatrician based on Diagnostic and Statistical Manual of Mental Disorders, 5th Edition (DSM-5) criteria will be considered for the study. DSM-5 is the handbook used by healthcare professionals as the guide to the diagnosis of mental disorders including ASD.

Inclusion criteria

1. Children aged 15-48 months
2. Children meet cut off score for Autism Spectrum Disorders (ASD) on Autism Diagnostic Observation Schedule-2 (ADOS): The Autism Diagnostic Observation Schedule (ADOS) is a semi-structured assessment of communication, social interaction, and play (or imaginative use of materials) for individuals suspected of having autism or other pervasive developmental disorders. The ADOS consists of a toddler module and four other modules, each of which is appropriate for children and adults of differing developmental and language levels, ranging from nonverbal to verbally-fluent. The ADOS consists of standardized activities that allow the examiner to observe the occurrence or non-occurrence of behaviours that have been identified as important to the diagnosis of autism and other pervasive developmental disorders across developmental levels and chronological ages.
3. Parent(s) is/are willing and able to give informed consent

4. Families with at least one parent who is digitally literate with the home use of the internet and access to Wi-Fi
5. The same parent(s) or caregiver(s) in attendance for most intervention sessions and all review sessions in order to monitor performance across outcome measures

Exclusion criteria

1. Participants not having access to the internet will be excluded
2. Received or receiving other treatment or interventions (*Note: this is an exclusion criterion but not a withdrawal criterion*)
3. Children with genetic and other associated auditory or visual impairment and/or seizure disorders

Program Implementation

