Midpoint IIP review: Therapists will review the child on the individualized intervention plan (IIP) developed after baseline assessment and plan for further intervention.

Final Reviews and Assessments: Visit 12 to 14

The final reviews and assessments will be conducted across three sessions, which can take place in any order depending on the participant's availability and therapist's schedule.

Final Review with Therapist: The child will be evaluated on the baseline assessment measures. Parents will also be given a parent satisfaction survey, cost survey and FEIQoL survey to complete. If parents are unable to complete the surveys during their clinic-based session, they will be sent the surveys through email or asked to answer the questions over a phone call. For children in the telerehab group, there will be a VC review in addition to the clinic-based assessment.

Nurse Assessment: The child will be evaluated on MSEL. The Parental Stress Index will be administered as part of this assessment.

Psychologist Assessment: VABS-III will be administered to the parent for this assessment.

Final Paediatrician review: Visit 15

[figure not shown]
This last paediatrician visit is for the paediatrician to share the reports on the evaluations, discuss progress and further needs of child and family.

Transfer to Early Intervention Programs

CDU provides interim therapy for children pending their enrolment into an EIPIC (or private early intervention service). Under normal circumstances, the child does not receive any intervention from EIPIC in the first 10 weeks on enrolment as the child is being assessed. In this transition period, the child continues to receive CDU intervention per standard clinical practice. As such, children in this study will continue to receive intervention for 10 weeks after EIPIC enrolment. Similarly, children who has been transferred to a private intervention service will continue to receive intervention per the study protocol as long as they have not started receiving intervention at the private service.

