Children also continue to remain as CDU patients under the care of their doctors until age 7, regardless of whether they have been enrolled to an EIPIC or private service. As such, study participants who have been transferred to an EIPIC will still be assessed per protocol for Midterm Progress Reviews and Final Reviews and Assessments. As far as possible, these assessments will be scheduled to coincide with their doctor's follow-up at the CDU as part of standard care.

Logic Model for Telerehab Program

Evaluation Framework

Literature Review

There is a dearth of published research on the use of telehealth in coaching for parents of children with autism spectrum disorders. A literature search found only two representative studies (Vismara et al, 2013 and Maedan et al, 2016) both from the United States and with small sample size.

One study followed eight families over a 12-week online video conference based intervention with three month follow up. Parents reported a better understanding of and appreciation for helping their children new skills, as well as increased confidence in addressing their child's needs and sharing information with other caretakers. The other described a similar Internet-Based Parent-Implemented Communication Strategies (i-PiCS) parental coaching program with 3 mother-child dyads and found positive changes in children's communication skills with the implementation of the strategies taught in coaching. As illustrated by the sample size <10 in each, neither previous study followed a rigorous RCT methodology but both studies highlighted the potential of telehealth as a feasible service-delivery option for parental coaching and called for further more robust studies of telehealth interventions with a greater diversity of participants.

Evaluation Questions

Effectiveness Trial

Primary Research Question: Is the tele-health intervention as effective as standard care in improving short and long-term outcomes for children and parents?

Process Evaluation

- How feasible and acceptable is the tele-health intervention?
- What features or conditions make the tele-health intervention more or less effective?
- What could be improved with acceptability, feasibility and scalability in mind?

Cost-Effectiveness

Is the tele-health intervention cost-effective (cost-saving) relative to standard care?

Indicators and Outcomes

Evaluation Question	Primary indicator required	Measurement & Reference	Expected change

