Patients will be recruited for the program after obtaining a preliminary diagnosis of ASD from the developmental paediatrician. ADOS-2 will be administered to confirm the diagnosis and thus participation in the research study. We will not be advertising this study to the public.

Pilot

An initial pilot feasibility study with 6 children and families will be conducted at the start of the project to identify any practical issues or weaknesses in the program or protocol before full scale evaluation.

Sample Size Calculation

The randomized trial is designed as a non-inferiority study to compare the changes in MSEL between 2 interventions. We expect that the change in MSEL score for the subjects in the new intervention arm will be slightly better than that in the control arm by 1.5 units. Assuming the SD of changes in MSEL score is 15 units, with 5 units as the non-inferiority margin, based on a one-sided test with 80% power and 5% significance level, it is sufficient to recruit 132 subjects (66 in each arm). We decided to recruit 200 subjects in total (100 in each arm) after considering withdrawals and lost to follow up. The computation was performed using a proprietary software programmed in R.

Randomisation Process and Blinding

Computer-generated randomisation will be used to randomly assign the participants to one of the intervention groups. Block randomisation will be used to allocate the recruited subjects into one of the interventions. A randomisation list will be generated by the study statistician and envelopes will be prepared. Although the allocation of intervention will be concealed and the study team will not know in advance which subject will receive which intervention, the blinding will not be possible once the intervention is assigned. Assessors of the initial and final MSEL were not told of the intervention status of the patient to avoid bias in outcome assessment. Blinding of the parents is not possible in the context of this study. Phone calls will be made if necessary to confirm appointments and/or before commencing consultation over video conference in the Telerehab group. Parents in both study arms will be encouraged to spend 2h per week in quality interactions with their children.

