Children who meet the inclusionary criteria will be randomly assigned to the standard or telerehab group of the study. Parents will be informed of the randomisation assignment and clinical diagnostic impression on ADOS. Baseline evaluation measures – Mullen's Scales of Early Learning (MSEL), Vineland Adaptive Behaviour Scales (VABS-III), Parenting Stress

Index (PSI-SF), Joint Engagement Rating Inventory (JERI) and FEIQoL (Families in Early Intervention Quality of Life) - will be completed for all.

Data Collection Time Points

The child and parents' skills will be recorded at 4 data points (baseline; 2 midterm reviews; final review) and progress tracked on the IIP, JERI and FSC. Parent questionnaires will be given at the end of the intervention to evaluate parents' experience with the technology used in the sessions, using a Likert Scale, and to evaluate their experience as *providers* of intervention services to their child. Video analyses will be performed by external raters. Inter-rater reliability will be calculated based on the assessments of raters (number of agreements/number of agreements plus disagreements). Hospital resource use pertaining to the intervention will be recorded at each point as well as healthcare expenditures and household resource use, travel expenses and caregiver time spent.

All clinical data will be collected in the case record form designed for the collection of data for the study. For the various assessment tools that will be used, data will be collected on the assessment tool itself, which will serve as the source of that data.

All data will be later transcribed to excel sheets or other relevant databases as soft data for statistical analysis. The data will be coded to remove any patient identifiers before sharing with the statistician for analysis.

Exit Review for Early Withdrawals

If the participant has completed their first block of intervention and requests to withdraw from the study before their final reviews and assessments (Visit 12 to 14), they will be presented with the option to come back to the clinic for an exit review before withdrawing. In the exit review, the child will be assessed on MSEL, parental stress index, parent satisfaction survey, cost survey, FEIQoL and VABS. Specific to the children in the telerehab arm, an additional video recording of parent-child interaction will be done through VC. However, participants can opt to not come back for the exit review and withdraw from the study immediately.

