Protocol deviation is defined as any divergence from what was pre-planned and approved by the institutional review board. As the study is conducted as part of routine care and operations, there are practical constraints that may cause protocol deviations to occur. Rescheduling of appointments by the parents (e.g. due to work constraints, child's sickness, other events) or defaulting appointments is inevitable. Hence, for per-protocol analyses, we will only exclude participants with major protocol deviation, which will be defined as participants who do not complete 80% of the intended therapy sessions allocated for their study arm. This means that a control arm participant must attend at least 8 out of 10 clinic-based sessions. For the remaining 2 sessions, participants can either be attending it through video-conferencing (due to the COVID-19 pandemic) or miss the appointment.

Quantitative Outcomes

For the randomized trial, since the study is a non-inferiority study, statistical analysis will be carried out on a per-protocol basis. Subjects with any major protocol deviation as defined above will be excluded from the final analysis.

All demographic, clinical and cost characteristics will be analysed descriptively. Mean (SD) or median (range), whichever is more appropriate will be reported for numerical variables, while N (%) will be reported for categorical variables. 2-sample t-tests, or Mann-Whitney U tests will be used to compare the change of MSEL score between 2 arms. Mean difference and 95% CI will be estimated. If the lower boundary of the 95% CI is more than -5, non-inferiority will be declared. Changes in the quality of parent-child engagement, parental stress index score, and adaptive score will be compared by using either a 2-sample t-test, or a Mann-Whitney U test, whichever is more appropriate. Linear regression will be used to adjust for any covariates.

Cost-Effectiveness Analysis

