The comparator for this study will be the standard model of delivery for EI which are clinic-based (face-to-face) sessions with the patients and their primary caregiver. The **variable treatment component** between telerehab and the standard model of delivery is the number of video-conferencing vs clinic-based intervention sessions. The assumption is that all non-therapy related costs such as paediatrician reviews will be the same for subjects in both study arms.

Table 1: Variable components of care between standard and telerehab care model

	Standard Model	Telerehab Model
Clinic-based intervention (45mins + 15mins)	16 sessions	2 sessions
Video-conferencing (30mins + 15mins)	0 sessions	16 sessions
Total Therapy time	720mins + 240 mins (admin)	570mins + 270 mins (admin)

Analysis Approach

We will take on two approaches to calculate the ICER. First, is the use of patient-level data for cost-effectiveness analysis. Second, we will use estimates generated from analyses Monte Carlo simulation to estimate the cost-effectiveness through parameters (mean, standard errors) obtained from the study. This will be decided by the analyst with the justification for the approach documented.

Time Horizon

The time horizon considered will be the duration of the program (around 1 year), from enrolment till final review. The cost and outcomes data collected will be limited to the duration of the program. It will be hard to justify extrapolations and assumptions after the program after the patient has transited out of NUH CDU to EIPIC, where treatment frequency and intensity will be substantially variable.

Univariate sensitivity analysis

One-way sensitivity analysis will be performed to assess the impact of a change in parameters.

Probabilistic sensitivity analysis²

Probabilistic sensitivity analysis (PSA) will be performed by incorporating the degree of uncertainty for each parameter. This involves assigning a primary mean value for each model parameter (mean cost, number of visits, probabilities) and the distribution of possible values. Monte Carlo simulation was used to estimate mean expected costs and outcomes, and statistical measures of expected variance (SD) around the mean for 1,000 iterations drawn from the distributions defined.

Direct Healthcare Costs

Health sector cost

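### A child can have the final MSEL after outside therapy has begun and still count as per-protocol; exposure may differ by arm, and the direction of any bias is unknown

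*Combined protocol and SAP*

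**What the plan says.** Outside therapy bars entry: the exclusion list has "Received or receiving other treatment or interventions". A note beside it adds that this is not a reason for withdrawal.

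Under Transfer to Early Intervention Programs, therapy at the unit is described as interim until EIPIC or a private service takes over. EIPIC gives no therapy for its first 10 weeks, and "children in this study will continue to receive intervention for 10 weeks after EIPIC enrolment". After a private transfer, study therapy runs only until private therapy starts. The section then says that "study participants who have been transferred to an EIPIC will still be assessed per protocol for Midterm Progress Reviews and Final Reviews and Assessments", timed where possible to the doctor's follow-up. This sentence names EIPIC only. For private services, continued assessment is inferred from the exclusion note and from the statement that children remain patients of the unit either way.

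Annex 2 puts the course at 40 to 60 weeks. Qualitative Data Collection and Annex 1 both foresee families moving on to other services, the former before the programme is complete.

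On analysis, Protocol Deviation and Per-protocol Analysis says "we will only exclude participants with major protocol deviation, which will be defined as participants who do not complete 80% of the intended therapy sessions". Quantitative Outcomes analyses MSEL per-protocol and declares non-inferiority if the lower 95% limit exceeds -5. It plans no all-randomised analysis, and its regression adjustment names no covariates. The exit review, which includes MSEL, VABS and PSI, is offered only to participants who ask to withdraw after completing their first block.

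**The concern.** A per-protocol analysis in a non-inferiority trial is meant to show what the assigned programme does when it is received largely as intended. Here a child can complete enough sessions, start EIPIC therapy, be tested on the MSEL afterwards and be analysed as a clean outcome of the assigned arm. Nothing in the analysis separates such children: there is no censoring rule, named covariate, sensitivity analysis or all-randomised companion.

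At stake is attribution. A non-inferiority verdict could describe telerehab plus an unmeasured amount of other therapy against clinic sessions plus a possibly different amount. Without start dates by arm, nobody could tell afterwards which way this had moved the result.

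**Working it through.** **1. The plan's own figure.** Sample Size Calculation gives: "Assuming the SD of changes in MSEL score is 15 units, with 5 units as the non-inferiority margin", telerehab "slightly better than that in the control arm by 1.5 units", one-sided 5% and 80% power.

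n per arm = 2 × [15 × (z0.95 + z0.80) / (5 + 1.5)]² = 65.85, rounded up to 66, or 132 in total. This reproduces exactly, so the point does not rest on a sample-size error.

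**2. Who can be exposed and still be per-protocol.** Session counts are from Annex 1.

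| | Block 1 | Block 2 | Block 3 | Block 4 | Total |
|---|---|---|---|---|---|
| Control | 6 | 4 | 6 | none | 16 |
| Telerehab | 6 | 4 | 2 | 6 | 18 |

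- Telerehab: 80% of 18 is 14.4, so 15 sessions. Only 6 + 4 + 2 = 12 are given by the end of block 3, so a child qualifies only within block 4.
- Control, by the worked rule of 8 out of 10: reached in block 2 (6 + 2).
- Control, by 80% of 16: 12.8, so 13 sessions, reached in block 3 (6 + 4 + 3).
- Control children have no study sessions during telerehab block 4.

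A control child can therefore qualify earlier and has a longer stretch before the final MSEL in which outside therapy could begin. The 80% rule removes some early transfers, but not evenly between arms.

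**3. What it could do to the decision.** SE = 15 × √(2/66) = 2.61. Under the 95% CI rule, taken as two-sided, P(declare non-inferiority) = Φ((d + 5)/SE − 1.96), where d is the observed expectation, telerehab minus control. The error rate is evaluated at a true difference of -5. The transfer rates and outside-therapy effects are assumptions; the documents give neither.

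| Assumed effect of outside therapy | d | False non-inferiority |
|---|---|---|
| None | -5 | 2.5% |
| Shrinks the deficit by 15% (30% of each arm exposed, half the deficit removed in them) | -4.25 | 4.7% |
| Shrinks it by 20% | -4.0 | 5.7% |
| Shrinks it by 30% (30% exposed, whole deficit removed in them) | -3.5 | 8.3% |
| Same gain added to an equal share of both arms | -5 | 2.5% |
| Adds 5 units, 20 percentage points more control children exposed: -5 − 5 × 0.20 | -6.0 | 1.0% |
| Adds 5 units, 20 points more telerehab children exposed: -5 + 5 × 0.20 | -4.0 | 5.7% |

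With 100 per arm (SE 2.12), shrinkage of 20% and 30% gives 6.8% and 10.5%. At the one-sided 5% level used for the sample size, with 66 per arm, the same shrinkage raises the error from 5.0% to 10.4% and 14.2%.

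If the design assumption of +1.5 is true, 20% shrinkage gives +1.2, and the chance of declaring non-inferiority falls from 70.2% to 66.1% (66 per arm, CI rule).

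**The case against.** Following children after transfer is defensible. The trial runs under routine conditions, asks about long-term as well as short-term outcomes, and loses less data this way. That stands: the later visit is not the flaw. The flaw is that its result enters the per-protocol analysis unmarked.

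A reader might infer that shared outside therapy must pull the arms together and so favour non-inferiority. The documents do not support that. It requires telerehab to be truly worse, similar exposure in both arms, and outside therapy that closes the gap rather than adding to both sides. None of these is shown, and the session schedule may place more exposure among controls, which works the other way. The 8.3% figure also needs outside therapy to remove the whole deficit in children who had already completed most of their sessions.

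Two further readings go too far. Time Horizon, in the cost-effectiveness section, declines to extrapolate "after the patient has transited out of NUH CDU to EIPIC, where treatment frequency and intensity will be substantially variable". That limits modelling beyond the programme; it does not concede that outcomes within it cannot be analysed. Nor does the costing ignore outside care: the indicator table counts parents' costs for other ASD-related interventions, and the cost survey asks about paid help. Neither source is planned for use in the MSEL analysis.

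**Conclusion.** The concern holds in a limited form. The stated rules admit a final MSEL measured after EIPIC therapy has begun (and, by inference, after private therapy) into the only planned analysis set, with exposure that may differ by arm. This follows from the text and needs no assumption.

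Direction and size are not established. They depend on a transfer rate and an outside-therapy effect that the documents do not give. Across the assumed scenarios at 66 per arm under the CI rule, the false non-inferiority rate runs from 1.0% to 8.3% against a nominal 2.5%. An unknown direction is itself a reason to measure exposure by arm.

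**What to change.** 1. Record the start date of any EIPIC or private therapy for every child in both arms, and report exposure by arm. For children already transferred, obtain the date retrospectively.
2. Before the final analysis, add to the per-protocol section an analysis in which an MSEL, VABS or PSI outcome measured after that date does not count.
3. Report it beside an all-randomised analysis that uses the scheduled final visit.
4. For children not yet transferred, offer the existing exit-review battery before outside therapy starts, and use it as a sensitivity outcome. It should not replace the main outcome: it shortens the course at measurement, its timing would depend on arm, and it contains no JERI rating.
5. Reconcile the 8-out-of-10 control rule with the 16-session control programme, since this decides when a control child enters the per-protocol set.

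The cost is amendment wording, one extra date per child and, for some, one earlier appointment. The stricter per-protocol set will be smaller and selects on an event after randomisation, and children measured early have shorter follow-up. Both analyses should therefore be shown. Children who have already transferred cannot be given a pre-transfer MSEL now.
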